	Grade 1	
• Continue study treatment.• Monitor kidney function, including creatinine, closely until values resolve to within normal limits or to baseline values.

Table 14 Guidelines for Management of Non-Hematologic Toxicities (cont.)

Event		Action To Be Taken
Pneumopathy, non-infectious (i.e., dyspnea, hypoxia, pulmonary infiltrates)	Grade 3 or 4	
Withhold obinutuzumab/rituximab and polatuzumab vedotin.Investigate etiology. Consult with a pulmonologist if immune etiology is suspected (refer to Atezolizumab Investigator's Brochure for guidance on investigations).Treat immune related pneumopathy with corticosteroids according to guidance provided in the Atezolizumab Investigator's Brochure.If symptoms have resolved and CT lung findings are clear, obinutuzumab and polatuzumab vedotin may be resumed at full dose.
	Grade 2	
Treat with corticosteroids according to guidance provided in the Atezolizumab Investigator's Brochure.
Other non-hematologic and non-immune- related toxicities (i.e., not described above), excluding alopecia, nausea, and vomiting	Grade 4	
Permanently discontinue study treatment.
	Grade 2 or 3	
Withhold study treatment.If there is improvement to Grade ≤ 1 or baseline, resume obinutuzumab/rituximab and polatuzumab vedotin at current dose.In case of laboratory abnormalities that are isolated, asymptomatic, and considered not clinically significant:
For Grade 3 laboratory abnormalities, study treatment may be resumed at the current dose upon improvement to at least Grade 2.For Grade 2 laboratory abnormalities, study treatment may be continued at the current dose at the investigator's discretion.

Table 14 Guidelines for Management of Non-Hematologic Toxicities (cont.)

CT=computed tomography; ECMO=extracorporeal membrane oxygenation; IRR=infusion-related reaction; PML=progressive multifocal leukoencephalopathy; MRI=magnetic resonance imaging; NCI CTCAE=National Cancer Institute Common Terminology Criteria for Adverse Events; NSAID=nonsteroidal anti-inflammatory drug; TLS=tumor lysis syndrome; TSH=thyroid-stimulating hormone; ULN=upper limit normal; VAD=ventricular assist device.

^a Graded according to NCI CTCAE Version 3.0.

^b *Atezolizumab may be withheld for a longer period of time (i.e., >12 weeks after event onset) to allow for corticosteroids (if initiated) to be reduced to the equivalent of ≤ 10 mg/day oral prednisone. The acceptable length of the extended period of time must be agreed upon by the investigator and the Medical Monitor.*

^c *If corticosteroids have been initiated, they must be tapered over ≥ 1 month to the equivalent of ≤ 10 mg/day oral prednisone before atezolizumab can be resumed.*

^d *Resumption of atezolizumab may be considered in patients who are deriving benefit and have fully recovered from the immune-related event. Patients can be re-challenged with atezolizumab only after approval has been documented by both the investigator (or an appropriate delegate) and the Medical Monitor.*

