4.6.2 Study Treatment Discontinuation

Study treatment should be permanently discontinued in patients who experience any of the following:

- Anaphylaxis, acute respiratory distress, or Grade 4 IRR
If a Grade 3 IRR is recurrent during the second and subsequent cycles, study treatment may be discontinued at the discretion of the investigator, following an individual benefit-risk assessment.
- Life-threatening adverse event
- Grade ≥ 3 non-immune-related adverse event that is considered to be related to study treatment and does not resolve to Grade ≤ 2 within 21 days
- Non-immune-related adverse event that is considered to be treatment related and requires study treatment to be withheld for >21 days
- Grade ≥ 3 immune-related adverse event that is considered to be related to atezolizumab or requires atezolizumab to be withheld for >42 days, unless approved by the Medical Monitor
- Any adverse event that meets criteria for permanent discontinuation per guidelines provided in Section 5.1

- Disease progression

Because of the potential for tumor flares with immunotherapies, resulting in early apparent radiographic progression (pseudoprogression/tumor immune infiltration), including the appearance of new lesions followed by delayed response (Wolchok et al. 2009), patients whose CT scans meet the criteria for disease progression may continue to receive study treatment at the discretion of the investigator and following discussion with the Medical Monitor, if certain criteria are met (see Section 4.1 for details). Cases of delayed pseudoprogression have also been described in patients with solid tumors treated with immunotherapies. In case of CT- findings suggestive for pseudoprogression in patients with persistent clinical benefit, the investigator should contact the Medical Monitor to discuss further patient management. Patients who continue to receive study treatment should have a CT scan repeated 4–8 weeks later.

- Pregnancy

In case of toxicity solely attributable to one drug of the combination requiring discontinuation, the other study drugs may be continued for patients experiencing clinical benefit as determined by the investigator after discussion with the Medical Monitor.

The primary reason for study treatment discontinuation should be documented on the appropriate eCRF.

Patients who discontinue study treatment will not be replaced, except as outlined below:

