	Grade 3	
First occurrence
 
 Withhold study treatment. Consult with a dermatologist. A biopsy should be considered unless contraindicated. If immune etiology is suspected, consider oral prednisone 10 mg or equivalent. If event is unresolved after 48–72 hours, administer oral prednisone 60 mg or equivalent. If there is improvement to Grade ≤ 1, resume obinutuzumab/rituximab and polatuzumab vedotin at full dose. Permanently discontinue obinutuzumab/rituximab and polatuzumab in the event of Stevens-Johnson syndrome or toxic epidermal necrolysis. 
Second occurrence
 
 Permanently discontinue study treatment.
	Grade 1 or 2	
 Continue study treatment Administer symptomatic therapy with antihistamines as needed If immune related toxicity related to atezolizumab is suspected, consider topical steroids and, for Grade 2, higher potency topical steroids if rash unresolved.
AST, ALT, or bilirubin increase	Grade ≥ 3 (or $\geq 10 \times$ ULN for patients with liver involvement)	
 Withhold study treatment Monitor liver function tests at least every 7 days while holding treatment. Investigate etiology. Consult with a hepatologist if immune etiology is suspected (refer to Atezolizumab Investigator's Brochure for guidance on investigations). For immune related hepatopathy: 
 Treat with corticosteroids following guidance provided in the Atezolizumab Investigator's Brochure Obinutuzumab and polatuzumab vedotin may be resumed at full dose at investigator's discretion. If immune etiology is unlikely and there is improvement to Grade ≤ 1, resume obinutuzumab/rituximab and polatuzumab vedotin at full dose. 
Permanently discontinue study treatment for life-threatening liver toxicity.

Table 14 Guidelines for Management of Non-Hematologic Toxicities (cont.)

Event		Action To Be Taken
AST, ALT, or bilirubin increase (cont.)	Grade 2 lasting >5–7 days	
 If immune etiology is suspected, treat with corticosteroids according to guidance provided in the Atezolizumab Investigator's Brochure.

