Ocular toxicity	Grade 3 or 4	
 Withhold obinutuzumab/rituximab and polatuzumab vedotin. Investigate etiology. Consult with an ophthalmologist. Treat immune-related toxicity attributable to atezolizumab with systemic corticosteroids according to guidance provided in the Atezolizumab Investigator's Brochure. If there is improvement to Grade ≤ 1, resume obinutuzumab/rituximab and polatuzumab vedotin at full dose.
	Grade 1 or 2	
 Investigate etiology. Consult with an ophthalmologist. Treat with topical corticosteroid eye drops. If symptoms persist, topical immunosuppressive therapy may also be considered.
Hypothyroidism		
 Investigate etiology. Consult with an endocrinologist (refer to Atezolizumab Investigator's Brochure for guidance on investigations). Start thyroid replacement hormone. Monitor TSH weekly. 
For asymptomatic and symptomatic patients with elevation of TSH:
 
 Continue study treatment.

Table 14 Guidelines for Management of Non-Hematologic Toxicities (cont.)

Event	Action To Be Taken
Hyperthyroidism	
For asymptomatic patients with TSH < 0.5 mU/L:
 
 • Perform TSH, free T4, and T3 tests every 4 weeks. 
For asymptomatic patients with TSH < 0.1 mU/L or symptomatic patients:
 
 • Consider consultation with an endocrinologist. • Administer methimazol as needed.
Hypophysitis (panhypopituitarism)	
 • Refer patient to endocrinologist. • Perform brain MRI (pituitary protocol). • Initiate treatment with 1–2 mg/kg/day IV methylprednisolone or equivalent and convert to 1–2 mg/kg/day oral prednisone or equivalent upon improvement. • Initiate hormone replacement if clinically indicated.
	
 • Refer patient to endocrinologist. • Perform brain MRI (pituitary protocol). • Initiate treatment with 1–2 mg/kg/day IV methylprednisolone or equivalent and convert to 1–2 mg/kg/day oral prednisone or equivalent upon improvement. • Initiate hormone replacement if clinically indicated. • For recurrent hypophysitis, treat as a Grade 4 event.

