5.3.3 Assessment of Severity of Adverse Events

The adverse event severity grading scale for the NCI CTCAE v4.0 will be used for assessing adverse event severity, with the exception of tumor flare reactions, which will be graded using NCI CTCAE v3.0. [Table 16](#) will be used for assessing severity for adverse events that are not specifically listed in the NCI CTCAE.

Table 16 Adverse Event Severity Grading Scale for Events Not Specifically Listed in NCI CTCAE

Grade	Severity
1	Mild; asymptomatic or mild symptoms; clinical or diagnostic observations only; or intervention not indicated
2	Moderate; minimal, local, or non-invasive intervention indicated; or limiting age-appropriate instrumental activities of daily living ^a
3	Severe or medically significant, but not immediately life-threatening; hospitalization or prolongation of hospitalization indicated; disabling; or limiting self-care activities of daily living ^{b,c}
4	Life-threatening consequences or urgent intervention indicated ^d
5	Death related to adverse event ^d

NCI CTCAE = National Cancer Institute Common Terminology Criteria for Adverse Events.

Note: Based on the most recent version of NCI CTCAE (v4.0), which can be found at:

http://ctep.cancer.gov/protocolDevelopment/electronic_applications/ctc.htm

^a Instrumental activities of daily living refer to preparing meals, shopping for groceries or clothes, using the telephone, managing money, etc.

^b Examples of self-care activities of daily living include bathing, dressing and undressing, feeding oneself, using the toilet, and taking medications, as performed by patients who are not bedridden.

^c If an event is assessed as a "significant medical event," it must be reported as a serious adverse event (see Section 5.4.2 for reporting instructions), per the definition of serious adverse event in Section 5.2.2.

^d Grade 4 and 5 events must be reported as serious adverse events (see Section 5.4.2 for reporting instructions), per the definition of serious adverse event in Section 5.2.2.

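### Section 4.6.2 and the Table 14 rows for ocular toxicity and pneumopathy give conflicting rules on restarting treatment after life-threatening events and severe atezolizumab-related immune events

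*Combined protocol and SAP*

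**What the plan says.** **Section 4.6.2 (Study Treatment Discontinuation)** opens its list with "Study treatment should be permanently discontinued in patients who experience any of the following". Two entries matter here:

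- "Life-threatening adverse event", with no qualifier in that bullet.
- A Grade 3 or higher "immune-related adverse event that is considered to be related to atezolizumab". The same bullet adds long atezolizumab holds and ends with a proviso for Medical Monitor approval. The wording leaves open whether the proviso covers the whole bullet or only the holds of more than 42 days.

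The section then makes an exception for toxicity that is due to one drug alone: "the other study drugs may be continued for patients experiencing clinical benefit as determined by the investigator after discussion with the Medical Monitor". Section 2 defines study treatment as all components together, so a permanent stop includes the anti-CD20 antibody and polatuzumab.

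**Section 5.1.7.2, Table 14** says:

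- Ocular toxicity, Grade 3 or 4: withhold, investigate, treat immune toxicity attributable to atezolizumab with steroids and, on improvement to Grade 1 or less, "resume obinutuzumab/rituximab and polatuzumab vedotin at full dose".
- Pneumopathy, Grade 3 or 4: "If symptoms have resolved and CT lung findings are clear, obinutuzumab and polatuzumab vedotin may be resumed at full dose".
- AST, ALT or bilirubin increase, Grade 3 or above, when immune-related: "Obinutuzumab and polatuzumab vedotin may be resumed at full dose at investigator's discretion". The same row requires a permanent stop for liver toxicity that is life-threatening.

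Table 14's opening general-guidance row says that when one drug is discontinued the other two may go on, for patients who benefit, after discussion with the Medical Monitor.

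**The concern.** An investigator whose patient recovers from a severe ocular or pulmonary event can find two instructions in the protocol: stop for good under Section 4.6.2, or restart under Table 14. No section says which takes precedence. Two sites could make opposite decisions for the same event and both cite the protocol.

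The first stake is patient safety. Ocular toxicity is part of the skin, oral mucosa and ocular signal that led the sponsor to stop enrollment and withdraw atezolizumab, and Section 5.1.6 asks sites to keep watching for it. The second stake is smaller. Section 6.3 tabulates treatment discontinuations for reasons other than progression and summarizes relative dose intensity. Both depend on which rule a site followed.

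**Working it through.** No sample size, rate or interval is involved, so the check sets the provisions side by side.

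| Provision | Life-threatening event | Atezolizumab-related immune event, Grade 3 or above | Medical Monitor step stated there? |
|---|---|---|---|
| Section 4.6.2 | Permanent stop | Permanent stop, subject to the proviso and the single-drug exception | Yes, in both exceptions |
| Table 14, ocular, Grade 3 or 4 | No exception; restart directed on improvement | Covered by name; restart directed on improvement | No |
| Table 14, pneumopathy, Grade 3 or 4 | No exception; restart permitted | Immune cause covered; restart permitted | No |
| Table 14, immune-related hepatic bullet | Row requires permanent stop | Restart permitted at the investigator's discretion | No |

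**Step 1: life-threatening events.** Table 16 defines Grade 4 as "Life-threatening consequences or urgent intervention indicated", and it applies to events that the CTCAE does not list. Some Grade 4 events are therefore life-threatening and some are not. For those that are, the ocular and pneumopathy rows contradict Section 4.6.2. The hepatic row agrees with it.

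**Step 2: immune events related to atezolizumab.** Section 4.6.2 does not bar restarting outright. It makes continuation depend on Medical Monitor involvement, either through the proviso (if that reaches the Grade 3 limb) or through the single-drug exception. All three Table 14 entries allow a restart without stating that condition.

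**Step 3: does the single-drug exception resolve it?** Not clearly. It needs toxicity due to one drug alone. Sections 1.5.1 and 5.1.6 assess the skin, oral and ocular constellation as specific to the three-drug combination.

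**Step 4: does the cross-reference resolve it?** Section 4.6.2 also lists any event that meets a permanent-stop criterion in Section 5.1. That brings Table 14's stops into the list. It does not let Table 14's restarts override the other entries.

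**Step 5: how do other Table 14 rows handle this?** Dermatologic, diarrhea/colitis, neurotoxicity and other non-immune events stop permanently at Grade 4. The hepatic and pancreatic rows name life-threatening cases. Myocarditis of Grade 3–4 is a stop, and continuing the remaining drugs needs Medical Monitor consultation. Nephritis of Grade 3 or 4 is a stop with Medical Monitor contact. The ocular and pneumopathy rows merge Grades 3 and 4 and contain none of these distinctions. The protocol does not say whether that is deliberate.

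**Step 6: is it still relevant?** Atezolizumab has been withdrawn, Section 3.1.4 says polatuzumab is no longer being given, and DLBCL consolidation has been removed. Obinutuzumab maintenance in FL continues, and Table 15 refers immune toxicities, naming hepatitis, pneumopathy and ocular toxicity, back to Table 14.

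**The case against.** The strongest reply is that the provisions can be read together. Table 14's general-guidance row carries a Medical Monitor condition close to that in Section 4.6.2, and individual rows need not repeat a table-wide rule. The pneumopathy and hepatic wording is permissive, so a mandatory stop elsewhere can still bind. Going on without atezolizumab was a documented sponsor decision (Section 1.5.5). Few treatments remain, and the affected analyses are descriptive.

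Much of this stands. A reader might infer that Table 14 never asks for Medical Monitor discussion; the general-guidance row shows otherwise. That row is framed around one drug being discontinued, however, and whether it governs these restart instructions is not stated. The permissive wording softens the pneumopathy conflict but not the ocular one, where the restart is an instruction. The sponsor's decision to continue without atezolizumab does not address restarting after a life-threatening event. The limited remaining exposure reduces the reach of the conflict but does not remove it during maintenance.

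**Conclusion.** Two stated stopping rules conflict. The conflict covers ocular toxicity and pneumopathy, for Grade 4 events that are life-threatening and for atezolizumab-related immune events of Grade 3 or above. It is sharpest in the ocular row. The hepatic bullet has a lesser gap, the absent Medical Monitor condition. The conclusion rests on study treatment meaning all components, as Section 2 defines it, and on there being no statement of precedence.

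Three stronger readings are not supported:

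- **Every Grade 4 event triggers the Section 4.6.2 stop.** Table 16 joins life-threatening consequences and urgent intervention with an or, and Section 5.2.2 defines life-threatening as immediate risk of death.
- **The hepatic row contradicts the life-threatening rule.** It contains that rule.
- **The 2 severe cases among 13 enrolled FL patients measure the problem.** They count a skin, oral and ocular constellation. The ocular components (scleritis and conjunctivitis) are not given a grade, and the count says nothing about pulmonary or hepatic events.

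The documents therefore give no frequency for the events in conflict. The issue warrants correction because it bears on patient safety and is cheap to settle; its effect on the analyses is slight.

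**What to change.** Reconcile Section 4.6.2 with the Table 14 rows for ocular toxicity and pneumopathy and with the immune-related hepatic bullet. The text should state:

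1. which provision governs when both apply;
2. whether the life-threatening rule applies to the ocular and pneumopathy rows;
3. whether Medical Monitor approval or discussion is needed before restarting under any of the three, and whether the general-guidance row supplies that condition;
4. how far the approval proviso in the Section 4.6.2 immune bullet extends.

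Table 15 should carry the same answer into maintenance. The choice of rule belongs to the sponsor's clinicians, and this review takes no position on it. The cost is amendment wording only, with no change to sample size, endpoints or analysis methods.

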5.1.7.3 Toxities during Maintenance Treatment

Table 15 provides guidelines for management of toxicities that occur during maintenance treatment.

Table 15 Guidelines for Management of Toxicities that Occur during Maintenance Treatment

Event	Action To Be Taken
Hematologic toxicity: Grade 3 or 4	
Withhold obinutuzumab/rituximab.Administer G-CSF for neutropenia per institutional guidelines.Administer RBCs or platelets as required.If there is improvement to Grade ≤ 2, resume obinutuzumab at full dose.If obinutuzumab is withheld for >42 days due to adverse event, permanently discontinue obinutuzumab/rituximab.
Non-hematologic toxicity: Grade ≥ 2	
For atezolizumab-related toxicities with possible immune etiology¹:
 
Follow guidelines presented in Table 14 for the management of atezolizumab-related toxicities with possible immune etiology (i.e., autoimmune colitis, hepatitis, pancreatitis, hypothyroidism, hyperthyroidism, pneumopathy, skin toxicity, or ocular toxicity). 
For non-immune mediated toxicities:
 
Withhold study treatment.If there is improvement to Grade ≤ 1 or baseline, resume obinutuzumab/rituximab at full dose.If study treatment is withheld for >42 days due to adverse event, permanently discontinue study treatment.

G-CSF=granulocyte colony-stimulating factor.

¹ Please refer to atezolizumab Investigators Brochure for additional information.

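### In maintenance, Table 15 tells the site to resume full-dose obinutuzumab after a life-threatening non-immune, non-hematologic event that recovers in time, whereas Section 4.6.2 requires a permanent stop

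*Combined protocol and SAP*

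**What the plan says.** Section 4.6.2 opens its list with "Study treatment should be permanently discontinued in patients who experience any of the following". One entry is simply "Life-threatening adverse event", with no condition on phase, causality or recovery. Another is "Non-immune-related adverse event that is considered to be treatment related and requires study treatment to be withheld for >21 days".

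Table 15 in Section 5.1.7.3 covers toxicity in maintenance. Its non-hematologic row starts at Grade 2 and has no ceiling. Atezolizumab-related events with a possible immune cause are sent to Table 14. For all others the site holds treatment and, on improvement to Grade 1 or less "or baseline, resume obinutuzumab/rituximab at full dose". The only permanent stop in that part of the row depends on duration: if the hold is longer than "42 days due to adverse event, permanently discontinue study treatment".

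Table 14, which Section 5.1.7.2 assigns to induction, has a matching class: "Other non-hematologic and non-immune- related toxicities (i.e., not described above), excluding alopecia, nausea, and vomiting". It divides that class in two. Grade 4 stops permanently; Grade 2 or 3 is held and resumed.

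Section 5.1.7 says that the tables set the maximum length of a toxicity delay.

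**The concern.** Table 15 is the toxicity table for the treatment that remains. Section 3.1.4 states that atezolizumab and polatuzumab vedotin are no longer given, Section 3.1.3.1 removes consolidation for diffuse large B-cell lymphoma, and Section 3.3.2.4 makes follicular lymphoma maintenance obinutuzumab alone. A site that opens the maintenance table after a life-threatening infection, bowel perforation or cardiac event finds an instruction to re-dose at full dose on recovery. Sections 5.1.1.6, 5.1.1.8 and 5.1.1.9 describe all three as obinutuzumab risks that can be fatal. Routine Internal Monitoring Committee assessments have ended (Section 3.1.4), so the written site rules carry more weight.

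What is at stake is the safety of a few patients. One descriptive output also depends on which rule the site follows: the Section 6.3 tabulation of discontinuations for reasons other than progression.

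**Working it through.** The plan gives no figure to reproduce. The check sets the two rules side by side for non-immune, non-hematologic events in maintenance.

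| Event | Table 15 | Section 4.6.2 | Result |
|---|---|---|---|
| Life-threatening; back to Grade 1 or less, or baseline, with hold of 42 days or less | Resume at full dose | Permanent stop | Conflict |
| Life-threatening; hold over 42 days | Permanent stop | Permanent stop | Agree |
| Related, not life-threatening; recovered, hold of 21 days or less | Resume at full dose | Hold limit not reached | Agree on the hold limit |
| Related, not life-threatening; recovered, hold of 22 to 42 days | Resume at full dose | Permanent stop under the hold limit | Conflict |
| Related; hold over 42 days | Permanent stop | Permanent stop | Agree |

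**First conflict (main).** Four readings might remove it; none does.

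1. Section 5.1.7 gives way to the tables on how long treatment may be delayed. It does not address whether a life-threatening event permits re-dosing.
2. Section 4.6.2 also brings in the stopping criteria of Section 5.1. That is a separate entry that adds triggers; it cancels none.
3. Section 4.6.2 lets the other drugs continue when one drug alone caused the toxicity. With obinutuzumab alone in maintenance, there is no other drug.
4. Table 14 cannot fill the gap. It is written for induction, and Table 15 borrows from it only for atezolizumab-related events with a possible immune cause.

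Table 15 keeps the hold-and-resume branch that Table 14 reserves for Grade 2 or 3, with the same recovery threshold, and omits the Grade 4 branch. No reason is given, so this looks like an omission.

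Grade 4 falls in the Table 15 row. Table 16 describes Grade 4, for events not listed in NCI CTCAE, as "Life-threatening consequences or urgent intervention indicated". Grade 4 is therefore wider than life-threatening, and the conflict with Section 4.6.2 concerns the life-threatening events within it.

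**Second conflict (secondary).** The hold limits differ by 42 − 21 = 21 days, that is, for holds of 22 to 42 days. Here Section 5.1.7 does speak to the matter, since it assigns the maximum delay to the tables. The 21-day limit is also repeated in Table 14, an induction table built on 21-day cycles. Both point to 42 days as the intended maintenance limit, with the Section 4.6.2 entry left without a phase.

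**Exposure.** Thirteen patients with follicular lymphoma were enrolled (Section 6.1), which is the ceiling. The number still on maintenance is not stated. Assumption: 1 to 3. The amendment summary counts 3 remaining patients for a pharmacokinetic sample, but they need not be the same patients. No event rate is assumed.

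**The case against.** The strongest reply is that the protocol already has the stop. Section 4.6.2 applies in every phase, Table 15 is headed as guidelines, and some foreseeable obinutuzumab events have their own stops: anaphylaxis, acute respiratory distress and Grade 4 infusion reactions in Section 4.6.2, and hypersensitivity in Section 5.1.1.2. This stands as a limit on the size of the problem. It does not remove it, because Table 15 does more than stay silent: it gives the opposite instruction.

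Three stronger readings are tempting, and the documents do not support them.

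- *The rules disagree for every life-threatening event.* They do not. If the event has not recovered when the hold passes 42 days, Table 15 also stops treatment.
- *There is a third conflict*, with the Section 4.6.2 entry on a Grade 3 or higher "non-immune-related adverse event that is considered to be related to study treatment and does not resolve to Grade" 2 or less within 21 days. That entry times the resolution of the event; Table 15 times how long treatment is withheld. Maintenance doses are 2 × 28 = 56 days apart (Table 2), so an event soon after a dose can run for weeks before any dose is withheld. The two limits cannot be subtracted from each other.
- *The discontinuation table would shift by a stated number of percentage points.* One patient over a cohort size is the same for any reclassified patient, and without an event rate it measures no effect.

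**Conclusion.** Table 15 is wrong as written, and the point is minor. For a life-threatening non-immune, non-hematologic event in maintenance that recovers before the hold exceeds 42 days, it contradicts Section 4.6.2 and lacks the Grade 4 stop of the corresponding induction row. The 21-day against 42-day hold limit is a lesser wording mismatch in which the table limit is probably the intended one.

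A reader might infer that maintenance has no stopping rule for life-threatening events. That is not so: Section 4.6.2 supplies one. The defect is a contradictory instruction in the table that a site would consult.

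Few patients are exposed, on the assumption of 1 to 3 still on maintenance. The primary endpoint, PET-CT complete response at the end of induction, is assessed before maintenance and is unaffected. The conclusion rests on the text alone and does not depend on the assumed number. It covers only the non-immune part of the non-hematologic row; it does not claim that all limits in Section 4.6.2 and Table 15, including the hematologic row, would then agree.

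**What to change.** Two wording changes at the next amendment:

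- (a) Table 15, non-immune part of the non-hematologic row: add *Life-threatening event: permanently discontinue study treatment (Section 4.6.2).* Using life-threatening rather than Grade 4 matches the trigger in Section 4.6.2.
- (b) Section 4.6.2, hold-duration entry only: change the limit to *>21 days during induction or >42 days during maintenance (Table 15).*

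The cost is one added line and one edited entry, with no new assessments. Change (a) restores a rule that Section 4.6.2 already states. Change (b) lengthens only the maintenance hold limit in Section 4.6.2, which Section 5.1.7 already leaves to the table.
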